4.2 Gold standard test results at Main Visits

Gold standard testing was performed for CT, NG, BV, TV and *Candida albicans* on samples taken during the Main Visit as follows:

- CT/NG: For those participants scoring negative on the CT/NG risk score, a GeneXpert swab was stored and tested by GeneXpert in the onsite Rinda Ubuzima laboratory later during the study. This was to permit comparisons between syndromic management alone, CT/NG testing after risk scoring, and CT/NG testing on everyone. We did not perform a commercial CT/NG PCR test because the GeneXpert platform is a PCR-based platform with proven high sensitivity and specificity. We therefore considered the GeneXpert results to be gold standard results in our analyses.
- BV, TV, Candida albicans: Two vaginal polyester swabs per participant were collected at the Main Visit (but not at Additional Visits). In the lab, the swab head was cut using sterile scissors, stored in RNALater (ThermoFisher Scientific, Waltham, USA) at -80 degrees Celsius. Gold

standard qPCR tests were performed at the Institute of Tropical Medicine in Belgium, Antwerp, after study completion. For BV, we conducted qPCRs for *Gardnerella vaginalis*, *Atopobium vaginae*, and *Lactobacillus* genus, and we will use a vaginal health score as follows: $[log_{10} \text{ geq/ml} (Lactobacillus \text{ genus}) - log_{10} \text{ geq/ml} (G. vaginalis + A. vaginae)]$. This vaginal health score correlated well with the Nugent score in a large vaginal microbiota study in three African countries⁵. We used validated in-house qPCR assays for TV and *C. albicans*.

Gold standard test results using Main Visit samples	n/N¹ (%)
CT by GeneXpert (POCT performed on everyone)	
NG by GeneXpert (POCT performed on everyone)	
Lactobacillus genus qPCR log ₁₀ meq/ml: median [IQR]	
Gardnerella vaginalis qPCR log10 meq/ml: median [IQR]	
Atopobium vaginae qPCR log10 meq/ml: median [IQR]	
BV by vaginal health score	
Trichomonas vaginalis by qPCR	
Candida albicans by qPCR	

Abbreviations: AV = *Atopobium vaginae*; BV = bacterial vaginosis; CT = *Chlamydia trachomatis*; GV = *Gardnerella vaginalis*; IQR = interquartile range; NG = *Neisseria gonorrhoeae*; qPCR = quantitative polymerase chain reaction.

1. The denominator is the number of women who provided Main Visit samples that were tested and produced a valid test result. The denominator may differ slightly per infection due to missing samples and invalid test results.

The following table describes, per possible infection, in what case treatment must be given per protocol. As mentioned before, the Rwandan guidelines include VDS algorithms that do not use risk scoring but use a pelvic examination to distinguish between mucopurulent cervical discharge and/or cervicitis (which is to be treated for CT/NG/TV) and non-muco-purulent vaginal discharge (which is to be treated for BV/TV/Candidiasis). We have decided to not take these algorithms into account.

Treatment given for:	WHO Syndromic Management	Rwandan Syndromic Management	WISH procedures	Gold standard procedures
СТ	Given with VDS and high risk / high local prevalence ¹ ; given with PID (after LAP) ²	Given with VDS and positive risk score ³ ; given with PID (after LAP) ² ; given as presumptive FSW treatment if asymptomatic ⁴	Positive for CT GeneXpert test performed after risk-scoring ⁵	Positive CT GeneXpert test (test performed on everyone)
NG	Given with VDS and high risk / high local prevalence ¹ ; given with PID (after LAP) ²	Given with VDS and positive risk score ³ ; given with PID (after LAP) ² ; given as presumptive FSW treatment if asymptomatic ⁴	Positive for NG after GeneXpert test performed after risk-scoring ⁵	Positive NG GeneXpert test (test performed on everyone)
TV	Given with VDS; covered with PID (after LAP) ²	Given with VDS no matter the risk score ³ ; covered with PID (after LAP) ² ; given as presumptive FSW treatment if asymptomatic ⁴	TV OSOM test	Positive qPCR test for Trichomonas vaginalis
UTI	NA	Treated based on reported symptoms	Positive urine dipstick test after reported symptoms ⁶	ND
BV	Given with VDS; covered with PID (after LAP) ²	Given with VDS and negative risk score ³ ; covered under VDS with positive risk score and PID (after LAP) ²	EcoCare pH swab (all pH ≥ 5.0 results treated)	Positive vaginal health qPCR DNA tool for BV ⁷

 ⁽As calculated by Log₁₀(*Lactobacillus* genus) – Log₁₀(*G. vaginalis* + *A. vaginae*). This DNA tool has a sensitivity and specificity comparable to the Nugent score. Further explained in the article by Jespers V, Crucitti T, [name] J et al. "A DNA tool for early detection of vaginal dysbiosis in African women." Res Microb 167.2 (2016): 133-41.

	on examination ⁸	or without notion of	algorithm after	
		recurrence) on	risk-scoring ⁹	
		examination		
Candidiasis	Given with VDS	Given with VDS and	Given with typical	Positive qPCR
	and typical signs	negative risk score ³	signs and	test for Candida

- 6. UTI POCT was performed if the participant reported typical symptoms. The dipstick was considered positive if it had at least 1+ leucocytes or was nitrite-positive, per Rwandan guidelines.
- As calculated by Log₁₀(Lactobacillus genus) Log₁₀(G. vaginalis + A. vaginae). This DNA tool has a sensitivity and specificity comparable to the Nugent score, and is further explained in the article: Jespers V, Crucitti T, [name] J et al. "A DNA tool for early detection of vaginal dysbiosis in African women." Res Microb 167.2 (2016): 133-41.
- 8. The WHO algorithm states in a note that only women with a positive RPR and no recent treatment should be treated. We hypothesized that no RPR results are available, which is often the case in Rwanda.
- 9. Syphilis testing was offered to the participant if she was positive for a Syphilis risk score (1 or more positive of: participant is pregnant; exchanged sex for money or goods in the past 12 months; has had a new sexual partner in the past 3 months; genital ulcers/blisters/sores were visible during the gynaecological exam).

5.2 Syndromic diagnoses based on spontaneously and structurally reported symptoms

We will use data from the sociodemographic interview and the pelvic and bimanual examinations to reconstruct hypothetical syndromic diagnoses, in the case rapid testing had not been available. Hypothetical reconstructions according to both the WHO and the Rwandan syndromic management guidelines will be reported. In this section, the symptoms that were spontaneously reported by participants, as well as the symptoms structurally reported by the participants during the face-to-face-interview, will be considered separately. The latter mimics real-life syndromic management, as in practice, clinicians ask exploratory questions on related symptoms after participants report suffering from a certain symptom. The following assumptions will be made:

- All women who report urogenital symptoms during the WISH study (spontaneously or structurally) would have sought treatment at local clinics (to be treated by syndromic management).
- All women reporting vaginal discharge of any kind will be considered at high risk of CT/NG due to high local prevalence (relevant for the WHO guidelines).
- All asymptomatic FSWs would have been regularly followed by local health clinics had they not participated in the WISH study (relevant for the Rwandan guidelines).

- All women with GUD would be treated for syphilis (relevant for the WHO guidelines which stipulate only to treat if a positive RPR is available and the patient has not been recently treated for syphilis; RPR testing is not commonplace in Rwanda).

WHO guidelines – based on spontaneously reported symptoms	n (%) N = 705
WHO syndromic diagnoses ¹ :	
- None	
- VDS (with or without LAP ²)	
Vaginal candidiasis	
- GUD without inguinal buboes	
 Inguinal bubo without signs of GUD 	
- LAP (with or without VDS) ²	
• PID	
Rwandan guidelines – based on spontaneously reported symptoms	n (%) N = 705
Rwandan syndromic management diagnoses ¹ :	
- None	
 VDS (with or without LAP²); with risk factors for CT/NG³ 	
 VDS (with or without LAP²); without risk factors for CT/NG³ 	
- GUD	
- Inguinal bubo	
- LAP (with or without VDS) ²	
• PID	
- Condylomata acuminata	
 Presumptive treatment for asymptomatic FSW⁴ 	
- UTI symptoms	

Abbreviations: FSW = female sex worker; GUD = genital ulcer disease; LAP = lower abdominal pain; PID = pelvic inflammatory disease; UTI = urinary tract infection; VDS = vaginal discharge syndrome.

1. Totals may be more than 100%.

2. Lower abdominal pain (with or without vaginal discharge) requires an abdominal and pelvic examination. If cervical motion, uterine, or adnexal tenderness is present, the participant is treated for pelvic inflammatory disease (and thus for CT/NG included). Hospital referral is required in the presence of alarming symptoms. When the participant reports both LAP and VDS, and is not diagnosed with PID, the VDS algorithm is followed.

- 3. If the participant reports vaginal discharge and (one of) her partner(s) has urethritis or she is positive for a risk score (2 or more positive of: age < 21; being single; 2 or more sexual partners in the past 12 months; new sexual partner in the last 3 months), the participant is to be treated for chlamydia/gonorrhea/*Trichomonas vaginalis*. If the participant reports vaginal discharge, none of her partners have urethritis, and she has a negative risk score (0 or 1 positive of: age < 21; being single; 2 or more sexual partners; new sexual partner in the last 3 months), the participant is to be treated for chlamydia/gonorrhea/*Trichomonas vaginalis*. If the participant reports vaginal discharge, none of her partners have urethritis, and she has a negative risk score (0 or 1 positive of: age < 21; being single; 2 or more sexual partners; new sexual partner in the last 3 months), the participant is to be treated for bacterial vaginosis/*Trichomonas vaginalis*/candidiasis.
- 4. Under the Rwandan guidelines, presumptive treatment for chlamydia/gonorrhea/*Trichomonas vaginalis* is given at the STI-related first visit if the patient is a female sex worker, but only in the absence of symptoms. If symptomatic, the normal algorithms are followed and the presumptive treatment is not given.

WHO guidelines – based on structurally reported symptoms	n (%)
	N = 705
WHO syndromic diagnoses ¹ :	
- None	
- VDS (with or without LAP ²)	
Vaginal candidiasis	
- GUD without inguinal buboes	
- Inguinal bubo without signs of GUD	
- LAP (with or without VDS) ²	
• PID	

Based on these syndromic diagnoses, participant would have received treatment	
covering the following urogenital infections ¹ :	
- None	
- CT/NG	
- TV/BV	
- Syphilis	
- Candidiasis	
Rwandan guidelines – based on structurally reported symptoms	n (%)
	N = 705
Rwandan syndromic management diagnoses ¹ :	
- None	
- VDS (with or without LAP ²); with risk factors for CT/NG ³	
- VDS (with or without LAP ²); without risk factors for CT/NG ³	
- GUD	
- Inguinal bubo	
- LAP (with or without VDS) ²	
• PID	
- Condylomata acuminata	
 Presumptive treatment for asymptomatic FSW⁴ 	
- UTI symptoms	
Based on these syndromic diagnoses, participant would have received treatment	
covering the following urogenital infections ¹ :	
- None	
- CT/NG	
- TV/BV	
- Syphilis	
- Candidiasis	
- UTI	
Abbreviations: BV = bacterial vaginosis; CT = Chlamydia trachomatis; FSW = female sex worker; GUD = gen	ital ulcer disease;

Abbreviations: BV = bacterial vaginosis; CT = *Chlamydia trachomatis*; FSW = female sex worker; GUD = genital ulcer disease; LAP = lower abdominal pain; NG = *Neisseria gonorrhoeae*; PID = pelvic inflammatory disease; TV = *Trichomonas vaginalis*; UTI = urinary tract infection; VDS = vaginal discharge syndrome.

1. Totals may be more than 100%.

2. Lower abdominal pain (with or without vaginal discharge) requires an abdominal and pelvic examination. If cervical motion, uterine, or adnexal tenderness is present, the participant is treated for pelvic inflammatory disease (and thus for CT/NG included). Hospital referral is required in the presence of alarming symptoms. When the participant reports both LAP and VDS, and is not diagnosed with PID, the VDS algorithm is followed.

- 3. If the participant reports vaginal discharge and (one of) her partner(s) has urethritis or she is positive for a risk score (2 or more positive of: age < 21; being single; 2 or more sexual partners in the past 12 months; new sexual partner in the last 3 months), the participant is to be treated for CT/NG/TV. If the participant reports vaginal discharge, none of her partners have urethritis, and she has a negative risk score (0 or 1 positive of: age < 21; being single; 2 or more sexual partners; new sexual partner in the last 3 months), the participant is to be treated for SV/TV/candidiasis.
- 4. Under the Rwandan guidelines, presumptive treatment for CT/NG/TV is given at the STI-related first visit if the patient is a female sex worker, but only in the absence of symptoms. If symptomatic, the normal algorithms are followed and the presumptive treatment is not given.

5.3 Comparisons syndromic management vs. WISH procedures vs. gold standard testing In this section, all hypothetical syndromic management (under WHO guidelines) individual algorithms and presumed treatments of STIs will be compared to the POCT results as performed during the WISH study, and to the gold standard results. For each outcome, sensitivity, specificity, positive predictive value (PPV) and negative predictive value (NPV) will be reported (see next page).

Procedure 1	Procedure 2	N pos/pos	N pos/neg	N neg/pos	N neg/neg	OR (95% CI) ¹	Sens. ²	Spec. ²	PPV ²	NPV ²
	(reference)	(= TP)	(= FP)	(= FN)	(= TN)	Fisher's p	(%)	(%)	(%)	(%)
Syndromic (WHO)	WISH procedures									
Any VDS (with or without LAP,	CT/NG (after RS) ³ by POCT, TV/BV						_			
typical or not for candidiasis)	by POCT, or treated for candidiasis								 	
Any VDS (with or without LAP,	CT/NG (after RS) ³ by POCT, TV/BV									
typical or not for candidiasis)	by POCT								 	
Any VDS (with or without LAP,	CT/NG (after RS) ³ by POCT									
typical or not for candidiasis)									L	
Any VDS (with or without LAP,	CT (after RS) ³ by POCT						_			
typical or not for candidiasis)									L	
Any VDS (with or without LAP,	NG (after RS) ³ by POCT						_			
typical or not for candidiasis)									 	
Any VDS (with or without LAP,	TV/BV by POCT						_			
typical or not for candidiasis)									 	
VDS (with or without LAP, typical	Treated for candidiasis									
for candidiasis)									 	
PID (with or without VDS, after	CT/NG (after RS) ³ by POCT, TV/BV									
LAP)	by POCT								Ļ	
PID (with or without VDS, after	CT/NG (after RS) ³ by POCT									
LAP)									Ļ	
PID (with or without VDS, after	TV/BV by POCT						_			
LAP)									Ļ	
GUD	Syphilis algorithm (after RS) ⁴						-			
									Ļ	
Would have received treatment	CT/NG (after RS) ³ by POCT									
for CT/NG ⁵									Ļ	
Would have received treatment	TV/BV by POCT								ł	
for TV/BV ⁵									ł	

Procedure 1	Procedure 2	N pos/pos	N pos/neg	N neg/pos	N neg/neg	OR (95% CI) ¹	Sens. ²	Spec. ²	PPV ²	NPV ²
	(reference)	(= TP)	(= FP)	(= FN)	(= TN)	Fisher's p				
Syndromic (WHO)	Gold standard	-		_				-		-
Any VDS (with or without LAP,	CT/NG (on everyone) by POCT, or									
typical or not for candidiasis)	TV/BV ⁶ /CA by qPCR									
Any VDS (with or without LAP,	CT/NG (on everyone) by POCT, or									
typical or not for candidiasis)	TV/BV ⁶ by qPCR									
Any VDS (with or without LAP,	CT/NG (on everyone) by POCT									
typical or not for candidiasis)										
Any VDS (with or without LAP,	CT (on everyone) by POCT									
typical or not for candidiasis)										
Any VDS (with or without LAP,	NG (on everyone) by POCT									
typical or not for candidiasis)										
Any VDS (with or without LAP,	TV/BV ⁶ by qPCR									
typical or not for candidiasis)										
VDS (with or without LAP, typical	CA by qPCR									
for candidiasis)										
Would have received treatment for	CT/NG (on everyone) by POCT									
CT/NG⁵										
Would have received treatment for	TV/BV ⁶ by qPCR									
TV/BV ⁵										
Syndromic (Rwanda)	WISH procedures		-							
Any VDS (with or without LAP,	CT/NG (after RS) ³ by POCT, TV/BV									
regardless of risk score ⁷)	by POCT, or treated for candidiasis									
Any VDS (with or without LAP,	TV/BV by POCT									
regardless of risk score ⁷)										
VDS (with or without LAP, positive	CT/NG (after RS) ³ by POCT, TV/BV									
risk score ⁷)	by POCT									
VDS (with or without LAP, positive	CT/NG (after RS) ³ by POCT									
risk score ⁷)										
VDS (with or without LAP, positive	TV/BV by POCT									
risk score ⁷)]			

Procedure 1	Procedure 2	N pos/pos	N pos/neg	N neg/pos	N neg/neg	OR (95% CI) ¹	Sens. ²	Spec. ²	PPV ²	NPV ²
	(reference)	(= TP)	(= FP)	(= FN)	(= TN)	Fisher's p				
VDS (with or without LAP, negative	TV/BV by POCT, or treated for									
risk score ⁷)	candidiasis									
VDS (with or without LAP, negative	TV/BV by POCT									
risk score ⁷)										
VDS (with or without LAP, negative	Treated for candidiasis									
risk score ⁷)										
Asymptomatic FSW ⁸	CT/NG (after RS) ³ by POCT, TV/BV									
	by POCT									
Asymptomatic FSW ⁸	CT (after RS) ³ by POCT									
Asymptomatic FSW ⁸	NG (after RS) ³ by POCT									
Asymptomatic FSW ⁸	TV by POCT									
GUD	Syphilis algorithm (after risk-									
	scoring) ⁴									
Typical UTI symptoms	Urinary dipstick (after reporting									
	typical UTI symptoms)									
Would have received treatment	CT/NG (after RS) ³ by POCT									
for CT/NG ⁹										
Would have received treatment	TV/BV by POCT									
for TV/BV ⁹										
Syndromic (Rwanda)	Golden standard	-		_		_				
Any VDS (with or without LAP,	CT/NG (on everyone) by POCT,									
regardless of risk score ⁷)	TV/BV ⁶ /CA by qPCR									
Any VDS (with or without LAP,	CT/NG (on everyone) by POCT,									
regardless of risk score ⁷)	TV/BV ⁶ by qPCR]			

Procedure 1	Procedure 2	N pos/pos	N pos/neg	N neg/pos	N neg/neg	OR (95% CI) ¹	Sens. ²	Spec. ²	PPV ²	NPV ²
	(reference)	(= TP)	(= FP)	(= FN)	(= TN)	Fisher's p				
VDS (with or without LAP, positive	CT/NG (on everyone) by POCT,									
risk score ⁷)	TV by qPCR									
VDS (with or without LAP, positive	CT (on everyone) by POCT									
risk score ⁷)										
VDS (with or without LAP, positive	NG (on everyone) by POCT									
risk score ⁷)										
VDS (with or without LAP, positive	TV by qPCR									
risk score ⁷)										
VDS (with or without LAP, negative	TV/BV ⁶ /CA by qPCR									
risk score ⁷)										
VDS (with or without LAP, negative	TV/BV ⁶ by qPCR									
risk score ⁷)										
VDS (with or without LAP, negative	CA by qPCR									
risk score ⁷)										
Asymptomatic FSW ⁸	CT/NG (on everyone) by POCT,									
	TV by qPCR									
Asymptomatic FSW ⁸	CT/NG (on everyone) by POCT									
Asymptomatic FSW ⁸	TV by qPCR									
Would have received treatment for	CT/NG (on everyone) by POCT									
CT/NG ⁹										
Would have received treatment for	TV/BV ⁶ by qPCR									
TV/BV ⁹										
WISH procedures	Gold standard	1				1	1	1	•	1
CT/NG (after RS) ³ by POCT	CT/NG (on everyone) by POCT									
CT (after RS) ³ by POCT	CT (on everyone) by POCT									

Procedure 1	Procedure 2	N pos/pos	N pos/neg	N neg/pos	N neg/neg	OR (95% CI) ¹	Sens. ²	Spec. ²	PPV ²	NPV ²
	(reference)	(= TP)	(= FP)	(= FN)	(= TN)	Fisher's p				
NG (after RS) ³ by POCT	NG (on everyone) by POCT									
Treated for PID (under WISH	CT/NG (on everyone) by POCT,									
procedures)	TV/BV ⁶ by qPCR									
TV by POCT	TV by qPCR									
BV by POCT	BV ⁶ by qPCR									
Treated for candidiasis	CA by qPCR									

Abbreviations: BV = bacterial vaginosis; CA = *Candida albicans*; CI = confidence interval; CT = *Chlamydia trachomatis*; FN = false negative; FP = false positive; FSW = female sex worker; GUD = genital ulcer disease; LAP = lower abdominal pain; NA = not applicable; NG = *Neisseria gonorrhoeae*; NPV = negative predictive value; OR = odds ratio; PID = pelvic inflammatory disease; POCT = point of care test; PPV = positive predictive value; RS = risk scoring; Sens. = sensitivity; Spec. = specificity; TN = true negative; TP = true-positive; TV = *Trichomonas vaginalis*; UTI = urinary tract infection; VDS = vaginal discharge syndrome.

- 1. By binary logistic regression.
- 2. As calculated by: sensitivity = TP / (TP + FN); specificity = TN / (TN + FP); positive predictive value = TP / (TP + FP); negative predictive value = TN / (TN + FN).
- 3. GeneXpert CT/NG testing was only offered if the participant was positive for the CT/NG risk score. The risk score was positive if at least one of the four following criteria was positive: 1) participant is currently pregnant 2) exchanged sex for money and/or goods in the past 12 months 3) reported a new sex partner in the last 3 months 4) abnormal cervicovaginal discharge during speculum exam and/or cervical motion/adnexal tenderness during bimanual exam. If a speculum/bimanual examination was not done, the last criterion was considered negative.
- 4. Syphilis testing was only offered if the participant was positive for the syphilis risk score. The risk score was positive if at least one of the four following criteria was positive: 1) participant is currently pregnant 2) exchanged sex for money and/or goods in the past 12 months 3) reported a new sex partner in the last 3 months 4) genital ulcers/blisters/sores visible during pelvic exam. If a pelvic examination was not done, the last criterion was considered negative.
- 5. Participant would have been received treatment covering CT/NG/TV/BV if she is positive for VDS (with or without LAP) and/or PID under the WHO guidelines. In the case of VDS, this is assuming all of our participants are at risk of CT/NG infection due to high local prevalence.
- 6. Further explained in the article by Jespers V, Crucitti T, [name] J et al. "A DNA tool for early detection of vaginal dysbiosis in African women." Res Microb 167.2 (2016): 133-41.
- 7. If the participant reports vaginal discharge and (one of) her partner(s) has urethritis or she is positive for a risk score (2 or more positive of: age < 21; being single; 2 or more sexual partners in the past 12 months; new sexual partner in the last 3 months), the participant is to be treated for CT/NG/TV. If the participant reports vaginal discharge, none of her partners have urethritis, and she has a negative risk score (0 or 1 positive of: age < 21; being single; 2 or more sexual partners; new sexual partner in the last 3 months), the participant reports vaginal discharge, none of her partners have urethritis, and she has a negative risk score (0 or 1 positive of: age < 21; being single; 2 or more sexual partners; new sexual partner in the last 3 months), the participant is to be treated for TV/BV/candidiasis.
- 8. Under the Rwandan guidelines, presumptive treatment for CT/NG/TV is given at the STI-related first visit if the patient is an FSW, but only in the absence of symptoms. If symptomatic, the normal algorithms are followed and the presumptive treatment is not given.
- 9. Participant would have received treatment covering CT/NG if she had VDS (with or without LAP) with a positive risk score as described under (8) and/or PID, or if she was an asymptomatic FSW. Participant would have received treatment covering TV/BV if she had VDS (with or without LAP), regardless of the result of the risk score described under (7), and/or PID, or if she was an asymptomatic FSW.

Outcome /		WHO sy	/ndrom	ic man	agement		R	wanda	n syndi	romic n	nanagem	ent		WISH procedures				Gold standard		
treated for	TP1	FP ¹	FN ¹	TN ¹	Sens. ¹	Spec. ¹	TP1	FP ¹	FN ¹	TN ¹	Sens. ¹	Spec. ¹	TP1	FP ¹	FN ¹	TN ¹	Sens. ¹	Spec. ¹	Negative	Positive
N = 705	Ν	Ν	Ν	Ν	%	%	Ν	Ν	Ν	Ν	%	%	Ν	Ν	Ν	Ν	%	%	Ν	Ν
CT ²																				
NG ²																				
CT and/or NG ²																				
TV ³																				
BV ³																				
BV and/or TV ³																				
Candidiasis ⁴																				
Syphilis⁵																				
UTI ⁶																				

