 Implement improved urogenital infection care services and monitor and evaluate these services 	 Monitoring and evaluation indicators, such as: Inputs: Procurement experiences/costs, infrastructure and training requirements; Activities/outputs: Numbers of clients counselled and risk scored, diagnostic tests conducted, infections diagnosed and treated, and referrals made; staff time required for each activity; time spent at the clinic for each client trajectory; Outcomes/impacts: Improvements of access to and quality of services (from client satisfaction survey, staff interviews).
Secondary objectives	Secondary endpoints
 Compare performance of syndromic management, POCT, and gold standard molecular testing for the diagnosis of NG, CT, TV, BV, and candidiasis. 	 Sensitivity, specificity, PPV, and NPV for: TV, BV: Syndromic vs POCT of everyone vs gold standard Candidiasis: Syndromic vs gold standard NG, CT: Syndromic vs POCT after risk scoring vs POCT (= gold standard) of everyone. The POCT test is a molecular test and is considered to be a gold standard in this SAP.

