5.4 Overview syndromic management and WISH procedures vs. gold standard testing

An overview table will be made to compare WHO and Rwandan syndromic management, and the procedures of the WISH study, with gold standard testing.

Abbreviations: BV = bacterial vaginosis; CT = Chlamydia trachomatis; FN = false negative; FP = false positive; FSW = female sex worker; GUD = genital ulcer disease; LAP = lower abdominal pain; NA = not applicable; NG = Neisseria gonorrhoeae; PID = pelvic inflammatory disease; POCT = point of care test; Sens. = sensitivity; Spec. = specificity; TN = true negative; TP = true-positive; TV = Trichomonas vaginalis; UTI = urinary tract infection; VDS = vaginal discharge syndrome.

1. Compared to gold standard testing (CT, NG, TV, BV, candidiasis) or WISH procedures reference test (Syphilis, UTI). Sensitivity calculated by TP / (TP + FN); specificity calculated by TN / (TN + FP).

2. Under WHO syndromic management, the participant is treated for CT/NG if she is positive for VDS (with or without LAP) and/or PID. Under Rwandan syndromic management, the participant is treated for CT/NG if she is positive for VDS and (one of) her partner(s) has urethritis or she is positive for a risk score (2 or more positive of: age < 21; being single; 2 or more sexual partners in the past 12 months; new sexual partner in the last 3 months), if she has PID, or if she is an asymptomatic FSW. Under WISH procedures, the participant is offered GeneXpert CT/NG POCT testing if she is positive for the WISH CT/NG risk score previously described, and treated based on the test results. Gold standard is defined as GeneXpert CT/NG POCT performed on everyone.

3. Under WHO syndromic management, the participant is treated for BV/TV if she is positive for VDS (with or without LAP) and/or PID. Under Rwandan syndromic management, the participant is treated for BV/TV is she is positive for VDS (no matter the Rwandan CT/NG risk score described under (2)), if she has PID, or if she is an asymptomatic FSW. Under WISH procedures, the participant is offered TV OSOM POCT testing and treated based on the test results, and is offered BV by pH testing and treated based on the test results (a pH of 5.0 or higher is treated, regardless of symptoms). Gold standard testing is defined as TV qPCR, and BV qPCR vaginal health score, as explained in section 5.1

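### In its visible text, SAP 5.3 puts its only 95% CI on an odds ratio that cannot be estimated in three CT/NG rows; the declared accuracy endpoints have point formulas only

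*SAP*

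**What the plan says.** The first secondary objective in SAP 1.1 is: "Compare performance of syndromic management, POCT, and gold standard molecular testing for the diagnosis of NG, CT, TV, BV, and candidiasis". The endpoints listed beside it are sensitivity, specificity, PPV and NPV.

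SAP 5.3 repeats this: "For each outcome, sensitivity, specificity, positive predictive value (PPV) and negative predictive value (NPV) will be reported". Each table row crosses a procedure with a reference and prints TP, FP, FN and TN. One column follows for the odds ratio with its 95% CI and Fisher's p, and then come the four accuracy measures as percentages. Footnote 1 gives the method for the odds ratio: "By binary logistic regression". Footnote 2 defines the four accuracy measures as ratios of cell counts and mentions no interval.

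On 5.4 the SAP says: "An overview table will be made to compare WHO and Rwandan syndromic management, and the procedures of the WISH study, with gold standard testing". That table has counts, sensitivity and specificity for the three strategies, with no interval, and it omits PPV and NPV.

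On the CT/NG reference, SAP 4.2 says: "We therefore considered the GeneXpert results to be gold standard results in our analyses".

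**The concern.** The interval is attached to a quantity that is not a declared endpoint. Very different pairs of sensitivity and specificity share the same odds ratio, so an interval on it does not say how precisely any endpoint is known. Fisher's p tests for association, which is not in question for a diagnostic procedure.

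The stated method also fails where it is most needed. The three WISH CT/NG rows evaluate risk scoring followed by testing. SAP 7.9 names the performance of that risk score as a secondary objective and makes a possible alternative score depend on it. In those rows sensitivity and NPV are the only accuracy measures left to estimate, and neither has a planned interval in the visible text.

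**Working it through.** The plan gives no precision or power figure for these endpoints, so there is nothing to reproduce first. The check has five steps.

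**1. Zero cells in the WISH CT/NG rows.** A woman is WISH-positive if her risk score was positive and her GeneXpert was positive (5.3, footnote 3). She is reference-positive if her GeneXpert was positive. By SAP 4.2 only risk-score-negative women had a stored swab tested later, so risk-score-positive women carry one and the same result on both sides. Hence FP = 0, and:
- specificity = TN/(TN + 0) = 100%
- PPV = TP/(TP + 0) = 100%
- OR = TP × TN/(FP × FN) = TP × TN/0, which has no finite value

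An assumed table for NG (85 cases, about 70% found) is TP 59, FP 0, FN 26, TN 620, total 705. One logistic fit stopped without converging at a log odds ratio of about 28 with a standard error of about 37,000. A GLM fit of the same table gave about 28 and 17,000. Where such a fit stops is arbitrary. Fisher's p can still be computed (8 × 10⁻⁶⁶).

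**2. The UTI-symptoms row.** Dipsticks were planned only for women with UTI symptoms, so a positive dipstick without symptoms should not occur and FN = 0. SAP 5.6 anticipates tests requested or performed in error, so this is probable, not certain. The row's denominator is not stated. With all women counted, sensitivity and NPV are both 100%. With only tested women counted, TN is also 0, sensitivity is 100% and NPV is 0/0.

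**3. What an odds ratio conveys.** OR = [Se/(1 − Se)] × [Sp/(1 − Sp)]. The protocol's BV figures (section 3.1: 71% and 76%) give (0.71/0.29) × (0.76/0.24) = 7.75. Sensitivity 50% with specificity 88.6% gives 7.75 as well, and so does 90% with 46.3%.

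**4. Width of the missing intervals.** Inputs: protocol 4.3 expects 60 NG, 75 CT and 75 TV cases per 500 women, and SAP section 2 gives 705 enrolled. Assumed cases are 705/500 × 60 = 84.6, about 85, and 705/500 × 75 = 105.8, about 106. The 77% TV sensitivity is from protocol 3.1. The other sensitivities are assumptions. Exact (Clopper-Pearson) 95% limits:

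| Measure | Count | 95% CI |
|---|---|---|
| NG, about 50% | 42/85 | 38.4-60.5% |
| NG, about 70% | 59/85 | 58.5-79.0% |
| NG, about 90% | 76/85 | 80.8-95.0% |
| CT or TV, 50% | 53/106 | 40.1-59.9% |
| TV test, 77% | 82/106 | 68.2-84.9% |

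SAP section 2 reports that later recruitment drew fewer risk-score-positive women, so CT and NG cases may be fewer. With half the cases the limits are 34.2-65.8% for NG (21/42) and 36.8-64.9% for CT (27/53). For TV, halving is only an assumption: 41/53 gives 63.8-87.7%.

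**5. What the printed counts allow.** Every marginal interval above can be computed from TP, FP, FN and TN. Paired comparisons need discordant counts.
- WHO versus Rwandan management, TV and BV: recoverable. WHO treats a woman "if she is positive for VDS (with or without LAP) and/or PID under the WHO guidelines", and Rwandan TV/BV treatment covers discharge "regardless of the result of the risk score described under (7), and/or PID, or if she was an asymptomatic FSW". The first group lies inside the second.
- WISH versus either guideline, combined CT/NG: recoverable. Every WISH-positive woman is reference-positive, and 5.3 crosses guideline treatment with the WISH result.
- WISH versus either guideline, TV, BV, candidiasis, and CT and NG separately: not printed. For CT and NG, 5.4 defines WHO treatment by discharge and/or PID, but 5.3 crosses PID only with combined outcomes.

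**The case against.** The strongest reply is that this is a matter of presentation. The protocol calls the primary objective descriptive, enrolment was set by budget, and both 5.3 and 5.4 print all four cells, so a reader can compute any marginal interval. The odds ratio fails for certain in only 3 of 59 rows (my count), the zero cell will be visible there, and sensitivity and NPV are unaffected. All of that stands, and it limits the point: no estimate is wrong. It does not explain why the plan computes an interval for an undeclared quantity and, as far as can be seen, none for the declared ones. A descriptive primary objective explains the absence of a power calculation, not the absence of intervals for a comparative secondary objective.

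Three stronger readings are tempting and are not supported.
- That the SAP plans no accuracy interval anywhere. Text between 4.2 and the treatment-definition table was not available, and a general methods sentence could stand there.
- That omitting paired differences between strategies is an error. SAP 1.1 declares the four accuracy measures and no differences.
- That the gap between WISH and syndromic management can be sized from the protocol's background figures, for example 77% against 14% for TV (63 points) or 71% against 10% for BV (61 points). The syndromic figures come from outside symptom-only data. The SAP's comparators are guideline-defined diagnoses rebuilt from spontaneous and prompted symptom reports, whose sensitivity could differ greatly.

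**Conclusion.** The point holds for the visible text of 5.3 and 5.4. Non-estimability in the three WISH CT/NG rows follows from the definitions and needs no assumption about the data; for the UTI row it is probable. The size of the precision gap depends on assumed case numbers. If the protocol's expectations scale to 705 women, intervals at 50% sensitivity are about 20 points wide for CT and TV and 22 for NG, and about 28 to 32 points for CT and NG with half the cases. Widths like these should appear beside the estimates. This is a reporting weakness in a secondary objective that should be corrected. It does not bias any result.

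**What to change.** 1. In 5.3, add exact or Wilson 95% CIs to sensitivity, specificity, PPV and NPV. In 5.4, add them to sensitivity and specificity.
2. Label the odds ratio and Fisher's p as association only, and omit the odds ratio where a cell is zero.
3. Mark specificity and PPV in the three WISH CT/NG rows as fixed by design, with no interval.
4. For the UTI row, state the denominator and mark sensitivity as fixed by design apart from ordering errors. NPV is fixed too if all women are counted, and undefined if only tested women are.
5. Optional: in 5.4, print the discordant counts for WISH versus WHO and WISH versus Rwandan management for TV, BV, candidiasis, and CT and NG separately, so that paired differences can be computed.

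The cost is a few lines of SAP text and code, with no new data. The downside is that wide intervals for the less common infections become visible.
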